### Appendix B. Data to be Collected

There are no protocol required assessments. The schedule below indicates requested data from medical charts where recorded per local institutional practice.

| Data to be collected   | Baseline       | Observation Period   |   |
|--|----------------|--|---|
|  |                | Treatment period (Blinicyto treatment - treatment start to 30 days after treatment completion) | Post treatment period (From 31 days after Blinicyto treatment completion to end of study) |
| Observation date   | X              | X  | X   |
| Informed Consent/Notification (as applicable)  | X              |  |   |
| Inclusion/Exclusion Criteria   | X              |  |   |
| Enrollment   | X              |  |   |
| Demographics   | X              |  |   |
| Medical History (including those ongoing at blinatumomab initiation): Co-morbidities | X a | X  | X   |
| Procedure HSCT   | X b | X  | X j  |
| ALL Medical History  | X b |  |   |
| Disease History (ALL)  | X b |  |   |
| NHL Medical History  | X b |  |   |
| Disease History (NHL)  | X b |  |   |
| Prior Anti-Cancer Therapies for Current Malignancy ALL                               | X b |  |   |
| Prior Anti-Cancer Therapies for Current Malignancy NHL                               | X b |  |   |
| Prior Radiology for Current Malignancy ALL   | X b |  |   |
| Prior Radiology for Current Malignancy NHL   | X b |  |   |
| Weight   | X              |  |   |
| Chemistry  | X c | X d   |   |
| Haematology  | X c | X d, g  |   |
| Coagulation  | X c | X d   |   |
| Immunology   | X c |  |   |
| Concomitant medications  | X k | X  | X e  |
| Concomitant Medication (Dexamethasone)   | X              | X  |   |
| IP Administration (Blinatumomab)   |                | X  |   |
| Frequency of Bag Changes   |                | X  |   |

| Data to be collected  | Baseline | Observation Period  |  |
|---|----------|---|--|
|   |          | Treatment period (Blincyto treatment - treatment start to 30 days after treatment completion) | Post treatment period (From 31 days after Blincyto treatment completion to end of study) |
| Hospitalisations  |          | X   | X f   |
| Treatment response  |          | X h  | X i,j   |
| End of IP Administration (Blinatumomab)                           |          | X   |  |
| Antibody  |          | X   |  |
| Product Complaints  |          | X   |  |
| Other Safety Findings   |          | X   | X  |
| Events – AEs and SAEs   |          | X   |  |
| Events – SAEs   |          |   | X l   |
| Anti-Cancer Treatment for current malignancy (Post Blinatumomab)  |          |   | X j   |
| Anti- Cancer Radiology for current malignancy (Post Blinatumomab) |          |   | X j   |
| End of Study  |          |   | X  |

- a From 1 year prior to start of Blincyto treatment (see note below)
- b Since Primary disease diagnosis (see note below)
- c From 30 days prior to start of Blincyto treatment (see note below)
- d Chemistry, Haematology and Coagulation assessments relating to Events (AEs/SAEs) should be documented in the CRF from the initiation of Blincyto and up to 30 days after Blincyto treatment completion
- e Concomitant medications to be collected only in the case of SAEs and data entered into concomitant medication form
- f Hospitalization information to be collected only in the case of SAEs and to be entered on SAE form only
- g Closest haematology pre-cycle and closest post cycle haematology assessments to be documented in the CRF
- h Treatment response to be documented in the CRF once pre-cycle and once post-cycle with the closest treatment response data pre and post cycle respectively
- i Response to be recorded in the subsequent anti-cancer therapy or anti-cancer radiology forms
- j For NHL subjects - These assessments will not be documented in the CRF
- k From 7 days prior to start of Blincyto treatment (see note below)
- l From 31 days after completion of treatment through to final chart abstraction, the start of another anti-cancer treatment, HSCT, or after 1 year, whichever is earliest - all SAEs to be reported. After the start of another anti-cancer treatment, HSCT, or after 1 year, whichever is the earliest, through to the end of study/final chart abstraction - only SAEs related to Blincyto and fatal SAEs to be reported.

Note: Medical history diagnosis dates/concomitant medication start dates may pre-date primary diagnosis dates. Furthermore, the diagnosis date of comorbidities may pre-date the disease diagnosis date.

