#### *Efficacy*

- Proportion of patients achieving CR (defined as < 5% bone marrow blasts, platelets > 100,000 cells per  $\mu\text{L}$ , and absolute neutrophil count > 1,000 cells per  $\mu\text{L}$ ) within 2 cycles of Blincyto treatment
- Proportion of patients achieving CR/CRh\*/Cri
- CR defined as < 5% bone marrow blasts, platelets > 100,000 cells per  $\mu\text{L}$ , and absolute neutrophil count > 1,000 cells per  $\mu\text{L}$ , or
  - CRh\* defined as  $\leq$  5% bone marrow blasts, platelets > 50,000 cells per  $\mu\text{L}$ , and absolute neutrophil count > 500 cells per  $\mu\text{L}$ , or
  - CRi defined as  $\leq$  5% bone marrow blasts and incomplete recovery of peripheral blood counts) within 2 cycles Blincyto treatment
- Proportion of patients receiving allogeneic HSCT. Defined for the subset of subjects who achieved CR.
- 1-year and 100-day mortality proportion after allogeneic HSCT. Defined for the subset of subjects who achieved CR.
- Relapse-free survival (RFS) time – defined as time from CR/CRh\*/CRi until relapse (proportion of blasts in bone marrow > 5% or blasts in peripheral blood after documented CR/CRh\*/CRi) or death. Defined for the subset of subjects who achieved CR.
- Disease free survival (DFS): defined as time from initiation of Blincyto (for minimal residual disease-positive [MRD+] patients at Blincyto initiation) until date of relapse or death
- Overall survival (OS) time – defined as time from initiation of Blincyto until death
- Proportion of patients with MRD among those who achieve CR/CRh\*/CRi within two cycles of Blincyto treatment - hematologic MRD detected by polymerase chain reaction (PCR) (or flow cytometry) at a level of  $1 \times 10^{-4}$  or higher.
- Efficacy outcomes (as described above) among patient subgroups defined by demographic and clinical factors (described in Section 9.7.2.3.4)

*Blinicyto utilisation & select health care resource use*

- Blincyto utilisation, for example:
  - Duration of Blincyto use (eg, number of completed cycles, total number of days of Blincyto administration)
  - Dosing pattern (eg, proportion of patients with step-up on day 8, number of cycles initiated, frequency of bag changes)
  - Proportion of patients with treatment changes (eg, interruption, discontinuation, dose reduction) as indicated by the SmPC after AEs (stratified by type of event)
- Select healthcare resource use, for example:

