### **9.7.2 Planned Method of Analysis**

All analyses will be descriptive. Continuous variables will be summarised by mean, median, standard deviation, 25th percentile, 75th percentile, minimum and maximum. Categorical variables will be summarised by number and percentage. For categorical outcomes, 95% confidence intervals will also be presented where appropriate. For time-to-event endpoints, Kaplan-Meier (KM) curves and estimates (median, 1st and 3rd quartile) of the time-to-event endpoint with 95% confidence intervals will be calculated, if estimable. Six, 12- and 24-month survival proportions and 95% confidence intervals will also be estimated. Tables will be presented for the total patient population (ie, those who meet the eligibility criteria and have at least one dose of Blincyto) split by adult and paediatric patients and for disease subgroups with 15 or more patients, as well as for the subset of patients with LFR. Safety and efficacy data will also be tabulated by the patient subgroups described in Section [9.7.2.3.4](#).

The Medical Dictionary for Regulatory Activities (MedDRA) version 24.1 or later will be used to code all adverse events.

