**9.7.2.3.3 Other Safety Analyses**

Subject incidence of serious adverse events (SAEs) that occur from 31 days after completion of Blincyto treatment until the start of another anti-cancer treatment, HSCT or for up to 1 year, whichever is earliest, will be tabulated overall and by system organ class and preferred term, and preferred term only. Subject incidence for SAEs will also be summarised by time interval (during Blincyto treatment and 3 month intervals after completion of treatment).

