#### 9.7.2.3.4 Subgroup Analysis

Specified outcomes will be presented by the following subgroups of interest:

| Subgroup  | Safety Outcomes | Efficacy Outcomes |
|---|-----------------|-------------------|
| Patient subgroups other than Adult RR Ph- ALL (potentially including MRD+ ALL, ph+ ALL, paediatric ALL, NHL)                            | Yes             | Yes               |
| Country   | Yes             | Yes               |
| Age groups, in years at initiation of Blincyto (Paediatric: 0-11, Adolescent: 12-17, Adult: $\geq 18$ and $< 65$ , Elderly: $\geq 65$ ) | Yes             | Yes               |
| Patients with HIV positivity or chronic infection with hepatitis B virus or hepatitis C virus at initiation of Blincyto                 | Yes             | -                 |
| Patients weighing less than 45 kg   | Yes             | -                 |
| Patients with recent allogeneic HSCT prior to initiation of Blincyto  | Yes             | -                 |
| Patients with prior allogeneic HSCT at initiation of Blincyto   | -               | Yes               |
| Patients with recent or concomitant treatment with other anti-cancer therapies (including radiotherapy)                                 | Yes             | -                 |
| Patients with recent or concomitant treatment with other immunotherapy  | Yes             | -                 |

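### Appendix B does not collect the post-treatment HSCT and relapse data that some reported efficacy endpoints need: for NHL by footnote j, and for ALL relapses that are not followed by further therapy

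*Protocol*

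**What the plan says.** **Endpoints.** Section 9.3.2.2 includes among the efficacy endpoints allogeneic HSCT, 100-day and 1-year mortality after it, RFS, DFS and OS. Relapse in RFS is a blast criterion ("proportion of blasts in bone marrow > 5% or blasts in peripheral blood after documented" remission), with death as the other event. HSCT, post-HSCT mortality and RFS are defined for patients who achieved CR, and DFS for patients who were MRD-positive at initiation.

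**Where they are reported.** Section 9.7.2 plans tables for the total treated population and for "disease subgroups with 15 or more patients", with 6-, 12- and 24-month survival proportions. Section 9.7.2.3.4 marks both safety and efficacy Yes for one row of groups other than adult R/R Ph- ALL, "potentially including MRD+ ALL, ph+ ALL, paediatric ALL, NHL".

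**What is collected.** Section 9.3 says that Appendix B summarises the data. Footnote h covers the treatment period: "Treatment response to be documented in the CRF once pre-cycle and once post-cycle". In the post-treatment column, footnote i says of response: "Response to be recorded in the subsequent anti-cancer therapy or anti-cancer radiology forms". Footnote j is attached to the post-treatment cells of HSCT, treatment response, anti-cancer treatment and anti-cancer radiology: "For NHL subjects - These assessments will not be documented in the CRF". That column has no relapse row and no haematology.

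**What the body promises.** Section 9.3.3 has ALL disease characteristics and treatment collected to end of study. The Study Design Schema lists disease characteristics and RFS after treatment.

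**Late SAEs.** Section 9.7.2.3.3 tabulates SAEs from day 31 "until the start of another anti-cancer treatment, HSCT or for up to 1 year, whichever is earliest".

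**The concern.** The collection schedule and the analysis sections do not match in two places.

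For NHL, the protocol plans efficacy output that includes HSCT and RFS but instructs sites not to record the post-treatment facts behind it. An NHL patient who reached CR and was transplanted two months after treatment would look, in the data, like one who was not. The same missing dates define when late SAEs stop counting.

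For ALL, the form that carries post-treatment response exists only if another therapy is given. A patient who relapses and receives nothing more has no such form. These are likely to be among the sickest patients, so the missing dates would not be missing at random. An analysis plan cannot recover a date that was never abstracted.

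**Working it through.** **Step 1: NHL, endpoint by endpoint, under footnote j.**

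| Endpoint | Source in Appendix B for NHL | Derivable? |
|---|---|---|
| CR, CR/CRh*/CRi within 2 cycles | Treatment-period response (footnote h, no NHL exemption) | Has a source, though the criteria are marrow and blood-count based |
| HSCT up to day 30 | Treatment-period HSCT cell, no exemption | Yes |
| HSCT after day 30 | Exempt (j) | No |
| 100-day and 1-year mortality after such an HSCT | HSCT date exempt (j) | No |
| RFS, relapse part after day 30 | Response and next therapy exempt (j) | No |
| RFS, death part; OS | Fatal SAEs to end of study (Section 11.2.2, footnote l); End of Study form | Yes |
| DFS | Defined for MRD-positive patients | Not an NHL endpoint in practice |

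**Step 2: NHL and late SAEs.** The stopping point is the earliest of next therapy, HSCT and 1 year. Footnote j leaves the first two undocumented. The site applies the cut-off when it decides what to report (footnote l), but related and fatal SAEs are still reported after it. In NHL those cannot be separated reliably from SAEs before the cut-off.

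**Step 3: ALL after day 30.** HSCT, next therapy and death are recorded. Relapse is recorded if a next-therapy or radiology form exists. Without one, a relapse could surface as a serious worsening of disease (Section 11.1.1) or as a loss of intended effect (Section 11.1.3). Neither route carries the blast criterion. Section 11.2.2 ends routine collection of unrelated non-fatal SAEs and of other safety findings at next therapy, HSCT or 1 year, while 24-month proportions are planned.

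**Step 4: possible size in RFS.** The protocol gives no figure for RFS, for NHL numbers or for the share of relapses without further therapy, so there is none to reproduce. The following is an illustration whose inputs are all assumptions:
- First-event times are exponential with median m = 7 or 18 months.
- A share p = 0.85 of first events are relapses.
- A share u = 0 to 0.40 of relapses get no further therapy, are missed, and count only at death.
- Survival after a missed relapse is exponential with median d = 1 to 6 months.

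Observed RFS at time t, for true RFS S(t) = 2^(-t/m), is

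S_obs(t) = S(t) + p·u·k·[2^(-t/m) − 2^(-t/d)], with k = (1/m)/(1/d − 1/m).

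At t = 12 months:
- m = 7: S = 2^(-12/7) = 0.3048.
  - u = 0.10, d = 1: k = 1/6; added 0.085 × (1/6) × (0.3048 − 0.0002) = 0.0043; observed 30.9%.
  - u = 0.40, d = 6: k = 6; added 0.34 × 6 × (0.3048 − 0.2500) = 0.112; observed 41.6%.
- m = 18: S = 2^(-12/18) = 0.6300.
  - u = 0.10, d = 1: k = 1/17; added 0.085 × (1/17) × (0.6300 − 0.0002) = 0.0031; observed 63.3%.
  - u = 0.40, d = 6: k = 0.5; added 0.34 × 0.5 × (0.6300 − 0.2500) = 0.065; observed 69.5%.

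A simulation of 400,000 event times agrees to within about 0.1 point. It puts the observed median at 7.1 to 9.6 months against 7.0, and at 18.1 to 21.3 against 18.0. Dating treated relapses 0.5 month late, with none missed, adds about 1 point at 12 months and 0.4 month to the median. With u = 0 and no lag the bias is zero.

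**The case against.** **NHL weighs little in practice.** The row includes NHL only as a possibility, Section 9.9 expects few off-label patients, and separate disease tables need at least 15. HSCT, post-HSCT mortality and RFS are limited to patients who achieved CR, so NHL patients to whom a marrow-based CR does not apply never enter those denominators. All this stands and lowers the weight. It does not remove the conflict: the 15-patient floor governs separate disease tables, not the total-population ones, and nothing takes an NHL patient classed as CR out of the latter.

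**A reader might infer that NHL efficacy is empty.** It is not. Footnote j touches four post-treatment cells only. Treatment-period response and HSCT, and deaths to end of study, are still collected.

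**A reader might infer that the late-SAE analysis fails for NHL.** That goes too far. Sites apply the cut-off when reporting, and concomitant medications recorded with post-treatment SAEs (footnote e) may reveal a next therapy. What is lost is the ability to check the cut-off and to separate later related or fatal events.

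**The body text governs, and Appendix B is a summary.** Sections 9.3 and 9.3.3 call for the endpoints and for ALL disease data to end of study, and the form fields are not shown. This is fair: the protocol does not prove that relapse goes unrecorded. But Appendix B is the protocol's detailed list of what is requested from charts, and a site following it would have no place for an untreated relapse. The two texts must be reconciled.

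**Conclusion.** The point holds as a mismatch between collection and analysis.

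For NHL, subsequent HSCT, mortality after it and the relapse part of RFS cannot be derived after day 30, despite the efficacy entry in Section 9.7.2.3.4. Response within two cycles and OS can. The SAE cut-offs cannot be checked.

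For ALL, a relapse without further therapy has no dedicated dated entry, contrary to Section 9.3.3 and the schema. This is the weightier half, because it bears on the main study population.

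It is tempting to conclude that RFS and DFS are overstated. The documents support only that they may be. The direction is upward, since a missed relapse counts at death or is censored. The size depends on a missed share that the protocol does not give, and it is limited because death is itself an event. The illustration gives 0 to about 11 points in 12-month RFS for a true median of 7 months and 0 to about 6.5 points for 18 months. The upper ends are the extreme of the assumed range, not estimates for this study.

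The endpoints are secondary and descriptive, so no test is affected. A change is still advisable, because published RFS and DFS would otherwise carry an unstated ascertainment gap.

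**What to change.** 1. **Section 9.7.2.3.4:** split the row. NHL now shares it with MRD+ ALL, Ph+ ALL and paediatric ALL, so deleting the efficacy entry there would remove efficacy for those groups too. Give NHL its own row, with efficacy restricted to response and OS.
2. **Total-population tables:** leave NHL out of the HSCT, post-HSCT mortality and RFS summaries, and state that its SAE cut-offs in Section 9.7.2.3.3 cannot be verified. The alternative to items 1 and 2 is to lift footnote j and collect the four items for NHL.
3. **Appendix B:** add a post-treatment field for ALL with relapse yes/no, date, and marrow or peripheral blasts as recorded in the chart. It should run to end of study whether or not further therapy is given, which brings the appendix into line with Sections 9.3.2.2 and 9.3.3.
4. **Where charts can no longer be re-abstracted:** report RFS and DFS with the stated limitation that relapses without further therapy may be undated.

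**Cost.** Items 1, 2 and 4 are wording, unless footnote j is lifted. Item 3 is one field in charts already reviewed every 4 months, but much of the work would be retrospective. Data collection was planned to start in Q1 2017 with new patients taken for 5 years, that is to about Q1 2022, and Amendment 9 is dated September 2022. Charts of patients who have completed follow-up or died would have to be reopened.

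### For NHL subjects the CRF omits the dates that close the post-treatment SAE window, so the window cannot be derived or verified and some related or fatal SAEs cannot be placed in it

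*Protocol*

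**What the plan says.** **Analysis.** Protocol Section 9.7.2.3.3 plans the "Subject incidence of serious adverse events (SAEs) that occur from 31 days after completion of Blincyto treatment", with the window running "until the start of another anti-cancer treatment, HSCT or for up to 1 year, whichever is earliest". It adds: "Subject incidence for SAEs will also be summarised by time interval (during Blincyto treatment and 3 month intervals after completion of treatment". No exception is made for NHL.

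**Collection rule.** Section 11.2.2 and footnote l of Appendix B tell sites to report every SAE from day 31 until the earliest of those same events. After that, only SAEs related to Blincyto and fatal SAEs are reported. Again there is no NHL exception.

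**Data collected.** In Appendix B, footnote j marks four post-treatment cells: "Procedure HSCT", treatment response, "Anti-Cancer Treatment for current malignancy (Post Blinatumomab" and "Anti- Cancer Radiology for current malignancy (Post Blinatumomab". The footnote reads: "For NHL subjects - These assessments will not be documented in the CRF".

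**Scope.** The subgroup table in Section 9.7.2.3.4 has a row for "Patient subgroups other than Adult RR Ph- ALL (potentially including MRD+ ALL, ph+ ALL, paediatric ALL, NHL", marked Yes for safety and for efficacy. Section 9.7.2 produces disease-subgroup tables only for groups of at least 15 patients. NHL patients belong to the total population whatever their number.

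**The concern.** The window in Section 9.7.2.3.3 closes at the first of three events. One of them, 1 year, is known from the date treatment ended. The other two, later anti-cancer therapy and HSCT, are left out of the CRF for NHL subjects once the post-treatment period begins. The analysis rule thus needs dates that the collection plan says will not be documented, and a statistical analysis plan cannot derive them.

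The same unrecorded dates also change what sites report. For an NHL subject, full SAE reporting stops at a date the database does not hold, while related and fatal SAEs continue to arrive. If a program simply ran the window to 1 year where the other dates are blank, a related or fatal SAE after later chemotherapy or a transplant would be counted as falling inside it. The 3-month summary has a similar weakness: for NHL subjects nothing in the CRF shows which intervals fall under full reporting and which under restricted reporting.

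**Working it through.** The protocol gives no figure on this point, so there is none to reproduce. The check sets the rules side by side and then bounds the result.

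**Step 1: which closing dates exist for an NHL subject**

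| Event closing the window | Up to 30 days after treatment | From day 31 |
|---|---|---|
| Later anti-cancer drug therapy | Concomitant medications (Section 9.3.3) | Not documented (footnote j); concomitant medications only if there is an SAE (footnote e) |
| Radiotherapy | Concomitant therapies (Section 9.3.3) | Not documented (footnote j) |
| HSCT | Recorded (this cell has no j) | Not documented (footnote j) |
| 1 year | Not reached | Follows from end of treatment |

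The gap opens on day 31, where the window starts. Section 9.3.3 does not fill it: regimens after Blincyto are listed for ALL only.

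**Step 2: which NHL subjects are affected**

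Assume sites follow Section 11.2.2 and footnote l. Take the SAEs recorded from day 31 to 1 year.

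- No SAE recorded: not a case.
- At least one SAE that is unrelated and non-fatal: a case, because such an SAE is reported only before the cut-off.
- Only related or fatal SAEs: undetermined, because these are reported on both sides of the cut-off. Section 11.2.2 counts doubtful relatedness as related, so this class is not confined to clear drug reactions.

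**Step 3: bounds**

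Let n be the patients in the table, x those with an SAE known to lie in the window, and k those who cannot be classified.

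- Lower bound = x/n; upper bound = (x + k)/n; width = k/n.
- Running the window to 1 year for all NHL subjects gives the upper bound.

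The documents give no number of NHL subjects. As an assumption, take n = 15 (the table threshold in Section 9.7.2) and x = 3:

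| k | Lower | Upper | Width (points) |
|---|---|---|---|
| 0 | 3/15 = 20.0% | 3/15 = 20.0% | 0 |
| 1 | 20.0% | 4/15 = 26.7% | 6.7 |
| 3 | 20.0% | 6/15 = 40.0% | 20.0 |
| 5 | 20.0% | 8/15 = 53.3% | 33.3 |

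For the total population, use the Section 9.5 sizes of about 200 and at most about 300:

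- k = 1: 1/200 = 0.5 points; 1/300 = 0.33 points.
- k = 3: 3/200 = 1.5 points; 3/300 = 1.0 point.

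If both dates were recorded, k would be 0 and the bounds would meet.

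**The case against.** A reader might infer that post-treatment SAE incidence cannot be computed for NHL at all. The documents do not support that. Section 9.7.2.3.3 plans a proportion of patients. The incidence and event rates in Sections 9.7.2.3.1 and 9.7.2.3.2 are tied to time on Blincyto, which footnote j does not touch. The site, which holds the chart, applies the cut-off when it abstracts, so most patients are classified correctly if sites comply. This narrows the problem to the undetermined class in step 2.

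A reader might also count every NHL patient who starts further therapy within a year as misclassified. That is too many: a patient with no SAE, or with an unrelated non-fatal one, is not misplaced.

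Other records may help. Each undetermined patient has a reported SAE, which brings concomitant medications (footnote e, no NHL exemption) and an individual case report (Section 11.2.2.1). Section 11.2.3 also allows the sponsor to ask for a discharge summary or chart extracts. These may recover some drug-therapy dates, but they do not guarantee an HSCT or radiotherapy date.

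An NHL table of these SAEs is not certain either. Section 9.7.2.3.3 asks only for overall, system organ class and preferred term tabulations. The subgroup sentence in Section 9.7.2 is general, the NHL wording is conditional, and 15 patients are needed. If NHL counts as off-label use, Section 9.9 expects few such patients. The primary and secondary adverse event endpoints stop 30 days after treatment and are unaffected.

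All of this limits the size of the point. The conflict between footnote j and the window rule remains.

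**Conclusion.** The point holds in a limited form. For NHL subjects the CRF leaves out the dates that end the Section 9.7.2.3.3 window and trigger the reporting switch in Section 11.2.2 and footnote l. The window cannot be derived or verified from the CRF, and patients whose only SAEs between day 31 and 1 year are related or fatal cannot be reliably assigned to it. The subject incidence can be bounded but not calculated as defined.

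Each such patient moves the total-population figure by about 0.33 to 0.5 points, and an NHL figure by 6.7 points if a table with n = 15 is produced. These sizes rest on site compliance with the reporting rule and on an assumed NHL group size; the number of undetermined patients is unknown and may be zero. This is a minor, easily corrected inconsistency. It does not undermine the main safety results.

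**What to change.** Choose one of two changes.

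1. **Record the dates.** Narrow footnote j so that, for NHL subjects, the CRF holds the date of first subsequent anti-cancer therapy (including radiotherapy) and the date of HSCT. End the window with them as for ALL. Cost: a small change to the data capture system, an amendment under Section 12.1, and some re-abstraction of charts, since data collection was planned to start in Q1 2017.
2. **Exclude and list.** State in Section 9.7.2.3.3 that NHL subjects are left out of the window analysis and that their post-treatment SAEs are listed separately. Cost: a sentence or two and a slightly smaller denominator.

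The second is the minimum and is enough if NHL subjects are few. The first is worth its cost if the group is likely to reach 15 and have its own table.
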